**b) Sample size determination and power analysis.** The effect size for APZ among *COMT* met-allele homozygotes in our preliminary data ( $d = 1.7$ ) and the genotype frequencies for the *COMT* val158met SNP were used to determine sample size and statistical power for Aim 1. Power was calculated iteratively with repeated estimation from the SPSS (IBM, Armonk, NY) MANOVA package. This analysis indicated that power to detect a *COMT* by tolcapone interaction in which tolcapone's effect size among val-allele homozygotes is 1.3 or greater is 0.8 with 30 subjects per genotype group. We anticipate that, out of 140 subjects with normal liver enzymes referred by the **ARC Clinical Intake and Assessment Core**, approximately 31 will carry the met/met genotype, 65 the val/met genotype, and 44 the val/val genotype. Accordingly, val/met and val/val subjects will be chosen for inclusion in this project or the other clinical project on the basis of an *a priori* randomization table. Those not chosen for inclusion will be referred to Project 4.

For Aim 2, the path coefficients  $a$ ,  $b$ , and  $c'$  will be used to estimate the strength of the causal relationship between each pair of variables (see **Figure 7**), and mediation will be determined by the significance of the joint ( $a * b$ ) product: does the indirect path from the independent variables through the mediator to the dependent variable (drinking) explain significant variance? Fritz and MacKinnon (80) have conducted large-scale simulation to form empirical estimates of power for mediated effects similar to Cohen's (81) original analysis of effect size for simpler regression problems. For 90 subjects and medium effect sizes ( $d = 0.5$ ) for the two arms of the indirect effect, power to detect a mediated effect is 0.8. Thus, power analyses for both Aims 1 and 2 suggest that a total  $N$  of 90 will yield  $\geq 0.8$  power to detect the hypothesized effects.

**Figure 7.** Proposed mediation pathway. The product ( $a * b$ ) estimates how much of the effects of *COMT* genotype and tolcapone on bar-lab drinking are due to cortical activation to the cue or stop-signal tasks.

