**c) Randomization plan.** *COMT* genotype will be used to prospectively randomize subjects to tolcapone or placebo medication. The *COMT* val/val genotype is more frequent among African-Americans (AA) than among European-Americans (EA), the two primary racial groups in the Charleston, SC area. In our preliminary data, 16% of subjects were AA and 83% were EA, consistent with the usual racial distribution of our studies. Val/val genotype frequency was 0.70 among AA and 0.25 among EA, consistent with dbSNP allele frequency estimates (Asian-Americans, who have comprised ~5% of our past study populations, have val/val frequencies similar to AA). To account for racial differences in val-allele frequency, we will stratify subjects by race (AA/Asian vs. EA) and *COMT* genotype (val/val, val/met, or met/met), and will then urn randomize subjects to tolcapone or placebo. Since some recent data suggest that the effects of both tolcapone (82) and *COMT* variation (83; 84) differ by sex, sex will be used as the urn variable within each of these six strata. The **ARC Biostatistics Core** statistician will oversee this process.

**d) Aim 1: Evaluate tolcapone and *COMT* val158met effects on drinking in the natural environment during six days of treatment.**

**1. Analysis and expected results.** Analyses for all aims will be conducted with consultation from the **ARC Biostatistics Core** statistician. The main dependent variable for Aim 1 will be drinking under natural conditions during days 1-6 (drinks per day). The general linear model (GLM) will be used to analyze the main effects of tolcapone and *COMT* genotype, as well as their interaction, on this variable. Pre-treatment drinking will be included as a covariate in these models, as will any salient demographic variables (e.g., age, cigarette smoking, family history of alcoholism). We predict that tolcapone, relative to placebo, will reduce natural drinking, and will do so to a greater extent among *COMT* val-allele homozygotes.

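### The Aim 1 model does not name race or sex, although randomization uses both, and no sensitivity analysis covers a tolcapone effect that differs by race, although val/val genotype tracks race

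*Combined protocol and SAP*

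**What the plan says.** Section B.5.c (Randomization plan) recognises that genotype depends on race. It reports: "Val/val genotype frequency was 0.70 among AA and 0.25 among EA". It adds: "In our preliminary data, 16% of subjects were AA and 83% were EA", and says that Asian-Americans, about 5% of past samples, resemble African-Americans (AA) rather than European-Americans (EA) in val/val frequency. Its response lies in the allocation: "To account for racial differences in val-allele frequency", "we will stratify subjects by race (AA/Asian vs. EA", crossed with the three genotypes to give six strata, with sex as the urn variable in each.

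Section B.5.d.1 (Aim 1) then tests tolcapone, COMT "genotype, as well as their interaction, on this variable". Pre-treatment drinking is a covariate, "as will any salient demographic variables (e.g., age, cigarette smoking, family history of alcoholism". Neither race nor sex is among the examples. No section specifies a race-by-tolcapone term or an analysis restricted by race.

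Section B.5.b states power of 0.8 if the "effect size among val-allele homozygotes is 1.3 or greater is 0.8 with 30 subjects per genotype group". Of 140 referrals it expects that "approximately 31 will carry the met/met genotype, 65 the val/met genotype, and 44 the val/val genotype". Section C.1.a expects about 20% racial and ethnic minorities.

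**The concern.** Two separate things are missing.

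First, race and sex shape the allocation, but the analysis does not commit to them. If a factor is balanced by design and predicts drinking, leaving it out keeps its variance in the residual. The standard errors are then too large for the design that was run.

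Second, genotype is observed and not assigned. Stratifying by race within genotype stops race from confounding the tolcapone effect inside a genotype, and it protects the interaction from a race main effect. It does not make the race mix alike across genotypes. If tolcapone works differently by race, for whatever reason, part of that difference will look like moderation by COMT.

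Moderation by COMT is the trial's central hypothesis. After a positive interaction, race is an obvious rival explanation, because the plan itself documents the link. Section B.1 starts data analysis once the blind is broken, so a check chosen at that stage would be post hoc.

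**Working it through.** **The plan's own figures.** Assumptions: 15 subjects per arm in each genotype, two-sided 0.05 (the plan states no alpha for this test), and an effect of 1.3 SD in val/val and 0 elsewhere. For the 1-df contrast of val/val against the mean of the other two genotypes:

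SE = √(4/30 + 4/60) = 0.447, and power = 0.82.

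This matches the stated 0.8. The 2-df interaction test gives 0.73. The plan does not say which form it will use, so both are shown below.

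**Race mix within genotype.** Assume Hardy–Weinberg proportions within race.
- AA/Asian: val frequency √0.70 = 0.837, so val/val, val/met and met/met are 0.70, 0.273 and 0.027.
- EA: val frequency √0.25 = 0.5, so 0.25, 0.50 and 0.25.

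Let p be the AA/Asian share. Three values can be drawn from the documents:
- 0.143, solved from 44/140 = 0.25 + 0.45p;
- 0.16, the preliminary AA share;
- 0.20, the expected minority share.

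At p = 0.16 the AA/Asian share of val/val is 0.16×0.70 / (0.16×0.70 + 0.84×0.25) = 0.112/0.322 = 0.348. The other genotypes follow in the same way. The last column is the val/val share minus the mean of the other two.

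| p | Genotypes of 140 (plan: 44/65/31) | AA/Asian share of val/val, val/met, met/met | Fraction entering the contrast |
|---|---|---|---|
| 0.143 | 44.0/65.5/30.5 | 0.318, 0.084, 0.018 | 0.268 |
| 0.16 | 45.1/64.9/30.0 | 0.348, 0.094, 0.020 | 0.291 |
| 0.20 | 47.6/63.7/28.7 | 0.412, 0.120, 0.026 | 0.339 |

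The two lower shares fit the plan's genotype counts better. The 20% figure is kept because the plan states it.

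**Effect on the test.** Let D be the difference in tolcapone effect between AA/Asian and EA subjects, in residual SD. D is assumed. With no COMT moderation, the contrast shifts by D times the fraction above, and the noncentrality is that shift divided by 0.447. Noncentral t and F give:

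| p | D | Shift (SD) | Type I error, 2 df | Type I error, 1 df |
|---|---|---|---|---|
| 0.16 | 0.5 | 0.15 | 5.8% | 6.2% |
| 0.16 | 1.0 | 0.29 | 8.4% | 9.8% |
| 0.20 | 0.5 | 0.17 | 6.1% | 6.6% |
| 0.20 | 1.0 | 0.34 | 9.7% | 11.6% |

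Simulations at the two lower shares, with race drawn at random, give 7–8% (2 df) and 8–9% (1 df) at D = 1.0.

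**Bound.** The 1-df contrast becomes significant at 1.99 × 0.447 = 0.89 SD. Race alone would need D = 0.89/0.339 = 2.6 to 0.89/0.268 = 3.3 SD to shift the estimate that far. To mimic the planned effect it would need 1.3/0.339 = 3.8 to 1.3/0.268 = 4.9 SD.

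**What each model change does.**
- Race main effect only: type I error at D = 1.0 is unchanged (p = 0.16: 8.4% and 9.8%).
- Race plus race by tolcapone: type I error returns to 5%, provided D is the same in every genotype and in AA and Asian subjects.
- A race main effect of 1 SD with D = 0: without race in the model the test runs at about 3–4% instead of 5%, and 1-df power is about 0.78, against 0.81 with race included.

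**The case against.** The harm depends wholly on D, and nothing in the documents suggests that D differs from zero. The plan cites possible differences in tolcapone effect by sex, not by race; race enters only through allele frequency. A D of 1.0 SD would be 77% of the planned effect (1.0/1.3). The highest error rates belong to a 1-df contrast that the plan never names, while the aripiprazole precedent used 2 df. The study is also described as a proof-of-concept probe.

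The check is weak too. At p = 0.16 about 14 AA/Asian subjects are expected among 90, only 3 or so of them outside val/val. The adjusted estimate would move by more than 0.28 SD by chance in 13–15% of trials with D = 0, and an EA-only estimate in 27–30%.

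All of this stands as a limit on the size of the problem and on what the check can show. It is why the primary interaction test should stay and the check should be descriptive. It does not remove the gap. Stratification leaves the race mix unequal across genotypes. The open covariate wording could supply a race main effect, but that does not touch this bias.

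**Conclusion.** The point holds, at modest size. Two allocation factors are not named in the Aim 1 model, and no planned analysis addresses a race-dependent tolcapone effect. About 0.27 to 0.34 of any such effect would pass into the val/val contrast. This rests on Hardy–Weinberg proportions within race, an AA/Asian share of 14–20%, 30 subjects per genotype and two-sided 0.05. The resulting error rates also rest on an assumed D.

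A reader might infer more: that a positive COMT-by-tolcapone result would be a race artefact, that the stratification has failed, or that listing race as a covariate would settle the matter. The documents support none of these. They give no estimate of a race difference, and D of 2.6 SD or more would be needed just to shift the estimate to the significance threshold. The stratification does what stratification can do within genotype. A race main effect leaves the leak as it was. Race could tip a borderline result; it could not by itself account for an effect of 1.3.

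**What to change.** Before unblinding, add to the Aim 1 plan:

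1. Name race (AA/Asian vs EA) and sex as main-effect covariates, because both were used in randomization. Say that this makes the standard errors match the design and is not a remedy for the race–genotype link. The cost is two degrees of freedom, and race and sex are already needed for the allocation.
2. Pre-specify one sensitivity model that adds race by tolcapone. Report its val/val-versus-carriers estimate and 95% CI beside the primary result, describing direction and size with no significance threshold.

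The downside of the second step is precision. At d = 1.3, power in that model is about 0.75 on 1 df and 0.65 on 2 df, against 0.82 and 0.73. The SE of the contrast rises from 0.447 to 0.484 at p = 0.16, so the change between models has SE √(0.484² − 0.447²) = 0.19, or about 0.2 SD. Its 95% CI of roughly ±0.4 is wider than the shift expected at D = 1.0. The plan should say that the model can reveal a large race effect but cannot rule out a modest one.

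An EA-only analysis is optional. If included, report it with its noise: the SE of the change from the primary estimate is about 0.28 SD.

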## B. Aripiprazole preliminary data and progress report

[figure not shown]
During the current ARC funding period, we tested this pharmacogenetic hypothesis by evaluating the interactive effects of *COMT* val158met variation and aripiprazole (APZ), a D2 partial agonist that is believed to stabilize cortical and striatal DA transmission, possibly by reducing both when they are upregulated (34) (although it also has serotonergic effects). We administered APZ to non-treatment-seeking subjects with early-stage alcohol dependence (i.e., individuals ages 21-40). To date, 60 subjects (mean age = 27, 75% male, average of 9 drinks/drinking day) have completed the study, in which they were randomized to APZ (titrated to 15 mg daily) or placebo for eight days, and completed alcohol cue-reactivity and stop-signal ( $N = 23$ ) fMRI tasks on day 7 and an alcohol self-administration paradigm (bar lab) on day 8. We used the cue-reactivity and stop-signal tasks because they assess motivated behavior and cognitive control and because PET studies suggest that these tasks strongly elicit cortical and striatal DA release (35; 36). We assessed the effects of APZ and *COMT* variation on the number of drinks, out of eight possible, that subjects chose to consume in the bar lab and on brain activation elicited by alcohol cues, as well as activation related to response inhibition.

Our preliminary data indicate that APZ trended toward reducing both drinks per drinking day during the first six days on medication ( $F(1, 57) = 3.15, p = .08$ ) and drinking in the bar lab ( $F(1, 57) = 2.50, p = .12$ ). However, the effect of APZ on bar-lab drinking was driven almost entirely by an interaction between medication group and variation at the *COMT* val158met SNP ( $F(2, 53) = 3.35, p < .05$ ; see **Figure 2**). Met-allele homozygotes who received APZ chose to consume, on average, two drinks, while those who received placebo chose to consume over seven drinks. While preliminary, this finding could account for some of the mixed findings from previous clinical trials of APZ for alcohol dependence (e.g., 37): APZ might be effective primarily for “early stage” individuals who are homozygous for the *COMT* met allele. Importantly, covarying for APZ-related side effects (e.g., sedation) did not reduce the statistical significance of this finding.

[figure not shown]

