**Figure 2.** Interaction between APZ and *COMT* val158met genotype on bar-lab drinking. APZ reduced drinking among met-allele homozygotes ( $F(1, 53) = 8.98, p = .004$ ), but was not significantly different from placebo for heterozygotes or val-allele homozygotes.

APZ and COMT val158met genotype also interacted in their effects on alcohol cue-elicited brain activation. A whole-brain analysis of this interaction identified a cluster in the right and medial OFC (Brodmann area [BA] 11) in which COMT genotype significantly moderated the effect of APZ on cue-elicited activation. APZ, relative to placebo, decreased cue-elicited OFC activation among met-allele homozygotes, but increased it among val homozygotes (see **Figure 3**). Further, OFC activation was positively associated with the number of drinks subjects consumed in the bar lab ( $r(60) = 0.26, p < .05$ ), and when it was added to the model that tested the interactive effects of APZ and COMT genotype on bar-lab drinking, the interaction was no longer significant ( $F(2, 52) = 2.00, p = .15$ ), suggesting that cue-elicited activation in this region mediated the effect.

**Figure 3.** Interaction between APZ and COMT val158met genotype on alcohol cue-elicited OFC activation. The color scale indicates voxels in which these factors moderated cue-elicited activation (thresholded, voxelwise, at  $z > 1.96$ ).

A subset ( $N = 23$ ) of the subjects in the current ARC study were also administered a response inhibition (stop-signal) fMRI task (38). For this task, activation to task trials on which subjects failed to inhibit a response was contrasted with activation to trials on which they successfully inhibited a response (i.e., unsuccessful vs. successful inhibitions). A whole-brain analysis indicated that, although APZ did not significantly affect activation associated with this contrast, COMT genotype did, such that, irrespective of medication, val-allele homozygotes, relative to heterozygotes and met homozygotes, displayed greater dmPFC (BA 9) activation during unsuccessful inhibition (see **Figure 4**). This finding is consistent with other reports that COMT val-allele carriers demonstrate dysregulated cortical activation indicative of compromised cognitive function (39). Activation of dmPFC did not mediate the interaction of APZ and COMT genotype on bar-lab drinking, but this conclusion is limited by the current sample size.

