**4. Expected mediation results:** We will test each of the vmPFC and OFC ALC vs. BEV coefficients and the dmPFC, dIPFC and IFG PSC values for the stop-signal contrasts (post- vs. pre-treatment) as individual mediators of the medication by genotype interaction on drinking (see **Figure 7**). To compare the effects of individual mediation by activation of any of the ROIs with the combined effects of cue-elicited and response-inhibition-related cortical activation, we will also test a multiple mediation model, in which the brain activation values described above are all tested in the same model. Using the SPSS AMOS package, we will model covariances between these ROI values (to partial out their shared variance), and will test whether the unique variance of the five ROIs collectively mediates the relationship between medication, genotype, and drinking to a greater extent than any individual ROI. To satisfy criteria for complete mediation, the medication and genotype variables must significantly predict the brain activation values, which must themselves predict significant variance in the drinking variables, and the medication by genotype interaction must be non-significant when the brain activation values are added to the model. If this interaction is still significant in the combined model, criteria for partial mediation can be satisfied if the indirect path between the interaction, the brain activation values, and drinking is also significant. *We predict that tolcapone, relative to placebo and to baseline, will reduce ALC vs. BEV activation of OFC and vmPFC and reduce dmPFC, dIPFC, and IFG activation for the successful vs. unsuccessful inhibitions and post-error slowing contrasts. Further, we predict that these effects will be greatest among val-allele homozygotes, that they will be related to drinking, and that they will mediate the medication by genotype interaction on drinking.*

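### *Complete* mediation is declared when the residual interaction is non-significant, with no limit on the direct effect; at about 15 per cell a residual of 75% of the planned effect is often non-significant

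*Combined protocol and SAP*

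**What the plan says.** Section B.5)e)4 sets three joint conditions for *complete* mediation. Medication and genotype must predict activation significantly. Activation must predict drinking significantly. Third, "the medication by genotype interaction must be non-significant when the brain activation values are added to the model". If that interaction remains significant, only *partial* mediation is available, provided the indirect path is significant.

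Section B.5)b) (Sample size determination and power analysis) gives a different basis for Aim 2: "mediation will be determined by the significance of the joint" a*b product. It names c' but sets no criterion for its size. Its power statements cover two things only. For the interaction, power when tolcapone's "effect size among val-allele homozygotes is 1.3 or greater is 0.8 with 30 subjects per genotype group". For mediation, with d = 0.5 "for the two arms of the indirect effect, power to detect a mediated effect is 0.8".

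In the aripiprazole preliminary data, after OFC activation was added to the model for the drug-by-genotype effect "on bar-lab drinking, the interaction was no longer significant". This was read as "suggesting that cue-elicited activation in this region mediated the effect".

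**The concern.** Because the first two conditions are shared in substance with any mediation claim, the p-value of the residual interaction alone decides between *complete* and *partial*. Failure to reject c' = 0 is then taken as evidence that c' is near zero. For given a and b results, a less precise estimate of c' makes the stronger label easier to earn.

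At stake is the central mechanistic claim of Aim 2. The trial could report that cortical activation fully accounts for the tolcapone-by-COMT effect on drinking while much of that effect remains unexplained. Some mediation would usually be real in such a trial; the word *complete* is what lacks support.

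**Working it through.** **Preliminary data (aripiprazole section).** The interaction was F(2, 53) = 3.35 and became F(2, 52) = 2.00, p = .15, with OFC activation added. Using f² = df1 × F / df2:

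- Before: 2 × 3.35 / 53 = 0.126, f = 0.356.
- After: 2 × 2.00 / 52 = 0.077, f = 0.277.
- Ratio: 0.277 / 0.356 = 0.78, so 78% remained by point estimate.
- Removing expected noise, the noncentrality F × df1 × (df2 − 2) / df2 − df1 goes from 4.45 to 1.85. The square root of the ratio is 0.64.
- The 95% CI for the residual noncentrality is 0 to 14.5. With N = 60 this is f from 0 to √(14.5/60) = 0.49, which includes the original 0.356.

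These f values summarise a 2-df test, so the comparison is approximate.

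**Planned trial: inputs.** N = 90 (B.1), three genotypes with 30 each (B.5)b)) and half per arm (C.1)a)) give about 15 per cell. The planned val/val effect is 1.3 SD (B.5)b)). Assumed: two-sided alpha 0.05, SD 1 within cell, effect in val/val only. The plan does not say whether the interaction is tested on 1 or 2 df, so both are shown.

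**Reproducing the stated power of 0.8.** For val/val versus the other two genotypes:

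- SE = √[(2/15)(1 + 1/4 + 1/4)] = 0.447; 1.3 / 0.447 = 2.91; power 0.82 on 84 df, close to the stated 0.8.
- The 2-df test has noncentrality 8.45 and power 0.73.

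**Precision.** Half-width = 1.989 × 0.447 = 0.889 SD; 0.889 / 1.3 = 68%. The Aim 1 section says: "Pre-treatment drinking will be included as a covariate in these models". If its correlation with the outcome is r = 0.4 (assumed), SE = 0.447 × √(1 − 0.16) = 0.410 and the half-width is 0.815 SD (63%). These figures are for the interaction before activation enters the model.

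**Chance that a real residual is non-significant (1 df / 2 df):**

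| Residual | r = 0 | r = 0.4 |
|---|---|---|
| 75% of 1.3 = 0.975 SD | 42% / 53% | 35% / 46% |
| 50% of 1.3 = 0.65 SD | 70% / 77% | 65% / 73% |

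**The whole rule, by simulation.** 20,000 trials per setting, one mediator, total effect 1.3 with 30% mediated: a*b = 0.39 and c' = 0.91, so b = 0.39 / a. Here a is the val/val effect on activation in SD. Each cell shows the false *complete* label among trials passing a and b, then in brackets over all trials (2 df / 1 df).

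| a | r = 0 | r = 0.4 |
|---|---|---|
| 1.3 | 64% / 53% (37% / 35%) | 56% / 45% (36% / 32%) |
| 0.8 | 52% / 40% (17% / 17%) | 42% / 30% (14% / 13%) |
| 0.5 | 22% / 14% (3% / 3%) | 5% / 2% (1% / 1%) |

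- At a = 0.5 the label is rare over all trials because the a leg passes in only 15% to 20% of them.
- Requiring a significant total interaction as well (r = 0) gives 53% / 45% (23% / 25%) at a = 1.3 and 45% / 36% (13% / 14%) at a = 0.8.
- Section B.5)e)1 excludes subjects with excess head movement. If cells fell to 12 (assumed, r = 0), the 2-df rate among trials passing a and b rises: 64% to 74% at a = 1.3. Over all trials it falls from 37% to 31% at a = 1.3 and changes little at a = 0.8 (17% to 16%) and a = 0.5 (3% to 4%).

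**The case against.** - **The rule has three conditions, not one.** This stands as a point about size. The 42% to 53% describes one condition; the rate for the full rule is lower, as the second table shows. It does not rescue the rule, since the other two conditions put no limit on c'.
- **The rates rest on an assumed a path.** This stands. The only figure the documents give for the arms of the indirect effect is d = 0.5. Read as the val/val effect on activation, it makes a false label rare (3% of trials, or 1% at r = 0.4).
- **A claim to explain the interaction presupposes a significant one.** This is fair, and it lowers the all-trial rates to 23% / 25% and 13% / 14% at a = 1.3 and 0.8.
- **The 53% goes with a set-up whose power is 0.73.** Set-ups near the stated 0.8 are 1 df without the covariate (42%) and 2 df at r = 0.4 (46%). A stronger covariate would help further: 23% to 33% at r = 0.6 and 15% to 23% at r = 0.7. The documents do not give r.
- **The combined five-region model was not simulated.** This is true; the rates are for a single mediator.
- **The preliminary report never says *complete*.** This is also true, and its residual interval is wide enough to include zero. The example shows lost significance being read as mediation; it does not establish how much of the effect remained.
- **The a*b product is already the stated test.** This supports the fix: the *complete*/*partial* rule adds a weaker inference to a sound one.

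**Conclusion.** The concern holds. The rule allows a claim of *complete* mediation with no evidence that the direct effect is small, and nothing else in the plan supplies that evidence. The logical fault needs none of the numerical assumptions.

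Its practical size does need them: two-sided alpha 0.05, about 15 per cell, an effect confined to val/val, one mediator, and assumed values for a and r. Under these, a false *complete* label with 30% mediated ranges from about 1% to 37% of all trials, depending mainly on a. This should be changed, but it is confined to the mediation conclusion of Aim 2.

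**What to change.** In section B.5)e)4:

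1. Base the mediation conclusion on the a*b product, as section B.5)b) already does, with a bootstrap 95% CI for each mediator.
2. Report the total medication-by-genotype interaction and c', each with a 95% CI.
3. Drop the labels *complete* and *partial*, or keep *complete* only when the CI for c' lies within a margin stated before unblinding.
4. As a clarification, state that the effect on activation in the first condition is the medication-by-genotype interaction.

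The same models are fitted, so the cost is wording. The downside is that a claim of full mediation may often be out of reach at N = 90. As an illustration, take a margin of ±0.65 SD (half the planned effect). Under true full mediation with a from 1.6 to 2.0 SD (assumed), the CI for c' lay inside it in 25% down to 0.3% of simulated trials without the baseline covariate. With the covariate at r = 0.4 the figures were 75% down to 6%.
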